1.7 Study Conduct

This study will be conducted in compliance with the protocol approved by the Institutional Review Board (IRB) or Independent Ethics Committee (IEC), and in accordance with GCP standards.

2 STUDY OBJECTIVES

2.1 Phase 1 Portion

2.1.1 **Primary Objectives**

- To evaluate the safety and tolerability of pamiparib for advanced cancer in Chinese patients
- To determine the recommended Phase 2 dose of pamiparib

2.1.2 Secondary Objectives

- To characterize the pharmacokinetics of pamiparib in Chinese patients
- To evaluate the clinical anti-tumor activity of pamiparib in Chinese patients with TNBC or high-grade epithelial, non-mucinous ovarian cancer (including fallopian cancer, or primary peritoneal cancer)
- To evaluate the relationship between pamiparib PK and clinical endpoints

2.1.3 Exploratory Objectives

•

2.2 Phase 2 Portion

2.2.1 **Primary Objectives**

• To evaluate the efficacy of pamiparib as measured by objective response rate according to Response Evaluation Criteria in Solid Tumors (RECIST), version 1.1 (RECIST V 1.1), by independent radiology review (IRR) in patients with advanced platinum-sensitive or platinum-resistant high grade, non-mucinous, epithelial ovarian cancer (including fallopian or primary peritoneal cancer), harboring germline *BRCA1/2* mutations

2.2.2 Secondary Objectives

- To evaluate the efficacy of pamiparib as measured by progression free survival, duration of response by both IRR and investigator review, and overall survival by investigator review
- To evaluate the efficacy of pamiparib as measured by the ORR by investigator review
- To evaluate the safety and tolerability of pamiparib
- To evaluate the efficacy of pamiparib as measured by disease control rate (DCR), best overall response (BOR) and clinical benefit rate (CBR) by both IRR and investigator review
- To evaluate the carcinoma antigen-125 (CA-125) response rate per Gynecological Cancer Intergroup (GCIG) for CA-125 changes
- To further characterize the PK of pamiparib

2.2.3 Exploratory Objectives

3 STUDY ENDPOINTS

3.1 Phase 1 Portion

3.1.1 Primary Endpoint

 Incidence of adverse events, overall and by severity, and incidence of SAEs according to National Cancer Institute Common Toxicity Criteria for Adverse Events, version 4.03 (NCI-CTCAE); laboratory abnormalities; changes in laboratory assessments, ECGs, and assessment of physical examinations.

3.1.2 Secondary Endpoints

- PK parameters of pamiparib and possibly its major metabolite(s) at selected time points: area under the plasma concentration-time curve from 0 to the last measurable concentration (AUC_{last}), maximum observed plasma concentration (C_{max}), and time to reach C_{max} (T_{max}); elimination half-life ($t_{1/2}$), apparent clearance (CL/F), and apparent volume of distribution during terminal phase (V_z/F) and other applicable parameters.
- Efficacy assessment by the investigator based on the RECIST, version 1.1:
 - ORR is defined as the proportion of patients who had confirmed CR or PR
 - DOR is defined as the time from the first determination of a confirmed overall response until the first documentation of progression or death, whichever comes first
 - DCR is defined as a BOR of CR, PR and stable disease (SD)
 - CBR is defined as a BOR of CR, PR and SD lasting \geq 24 weeks
 - PFS is defined as the time from first dose of study medication to the first documented disease progression or death due to any cause, whichever occurs first

3.1.3 Exploratory Endpoint

•

3.2 Phase 2 Portion

3.2.1 Primary Endpoints

• ORR as defined above in advanced HGOC patients by IRR

3.2.2 Secondary Endpoints

- DOR and PFS as defined above
- OS is defined as time from the first dose of study medication to the date of death due to any cause
- ORR as defined above in advanced HGOC patients by investigator review
- CA-125 response rate per GCIG criteria for CA-125 changes
- Incidence of AEs, overall and by severity, and incidence of SAEs; laboratory abnormalities; changes in laboratory assessments, ECGs, and assessment of physical examinations such as vital signs

- PK parameters of pamiparib and possibly its major metabolite(s) at selected time points: AUC_{last} , C_{max} , and T_{max}
- For patients participating in intensive PK sample collection: AUC_{0-12h} , C_{max} , C_{min} , and T_{max}
- DCR and CBR as defined above

3.2.3 Exploratory Endpoints

•

[figure not shown]
4 INVESTIGATIONAL PLAN

4.1 Overall Study Design

This is a Phase 1/2, open-label, multi-center study of pamiparib administered PO BID to adult Chinese patients with advanced solid tumors which have progressed despite standard therapy or for which no standard therapy exists.

The study will continue until the last patient has died, becomes lost to follow up, or withdraws from study, or until sponsor decides to terminate the study.

Figure 2. Schema of overall study design of Phase 1/2 study Pamiparib-102

Abbreviations: HGOC, high grade ovarian cancer; BID, twice daily

4.1.1 Phase 1 Portion

The Phase 1 portion of this study is designed to evaluate the safety, tolerability and PK profile of pamiparib in Chinese advanced cancer patients and to determine RP2D of pamiparib for Chinese patients. In the FIH study of pamiparib in Australia, the RP2D and MTD were determined to be 60 mg BID and 80 mg BID, respectively. In this study, three dose levels, 20 mg, 40 mg, and 60 mg BID, will be evaluated. The purpose of this study is to determine the RP2D and MTD, if any, of pamiparib in Chinese cancer patients. Dose escalation will follow a modified 3+3 dose escalation design.

Patients will be screened for eligibility up to 21 days prior to the first dose of pamiparib. The starting dose will be 40 mg/day (20 mg BID; see Section 1.5 for the justification of the starting dose level). The 23-day initial treatment cycle (Cycle 1) of each dose level will consist of a single administration of pamiparib (20 mg) on the morning of Day 1, followed by one day treatment-free period (Day 2) and a 21-day period of repeated drug administration (BID, once in the morning and once in the evening 12 hours \pm 2 hour apart, Days 3 to 23).

Safety evaluation of at least 3 patients completing one cycle of treatment at that dose level is required prior to determining the next dose level and dose regimen for the next cohort.

If a patient wishes to continue study treatment upon completion of Cycle 1, the patient can continue study treatment in 21-day Cycle 2 (with no treatment-free or rest period) and subsequent cycles, at the discretion of the investigator.

After the first patient in the first dose level receives the Cycle 1, Day 1 dose, subsequent patients in that cohort will not be dosed until the first patient has been observed for at least 24 hours to exclude unexpected acute toxicity. The continuous safety evaluation will be

performed by the sponsor, the coordinating investigator, and investigators. A Safety Monitoring Committee (SMC) will be established to determine the dose levels to be administered and dose regimen during dose escalation, and their decision will depend on the data available from the previous dose levels. The suggested dose escalation scheme is presented in Table 3.

Step	Daily dose (mg) ¹
1	20 BID
2	40 BID
3	60 BID

Table 3.Suggested Dose Escalation Scheme

1. The actual dose levels and dose regimens administered in each step will depend on the data available from the previous step, as determined by the Safety Monitoring Committee.

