screening. The ECG time points for pharmacokinetic sampling in conjunction with PK will be obtained as per Table 6. Patients should be in the semi-recumbent or supine position. If prolongation of QT or QT interval corrected for heart rate (QTc) is noted during the first 15 days, 12-lead ECGs will be performed weekly during Week 3 to Week 6, and then once every 3 weeks, on Day 1 of every cycle from Cycle 3 onwards, for the remaining duration of treatment

- 11. Disease assessment during the screening may be completed up to 28 days prior to the first dose of pamiparib. Afterwards, disease assessments will be performed once every 6 weeks ± 7 days after the first dose of pamiparib in the first year, then every 12 weeks ± 7 days thereafter to assess all known disease. For patients with treatment terminated prior to documentation of disease progression, they shall be subjected to CT/MRI radiographic assessment according to the previous visit assessment scheme, until 1) commencement of new treatment, 2) disease progression, 3) death or 4) termination of the study
- 12. After informed consent has been signed, but prior to study treatment, only SAEs should be reported
- 13. A CT scan or MRI scan of the chest, abdomen, and pelvis will be performed once every 6 weeks ± 7 days in the first year, then every 12 weeks ± 7 days thereafter to assess all known disease
- 14. For women of childbearing potential including those who have had a tubal ligation, urine or serum pregnancy test must be performed and documented as negative within 7 days prior to Cycle 1 Day 1, and urine pregnancy tests will be performed at each visit prior to dosing. A serum pregnancy test must be performed if urine pregnancy test is positive or equivocal
- 15. Baseline blood samples for all patients should be collected for retrospective germline BRCA1/2 mutation testing. Blood sample will be taken from each patient.
- 16. Archival tumor tissues will be collected, if available
- 17. The pharmacokinetic blood samples will be collected at the time points specified in Table 6
- 18. A single dose of pamiparib will be administered on the morning of Day 1 of Cycle 1. Multiple administrations will start on Day 3 (Cycle 1 only) or on Day 1 (Cycle 2 and onwards) and continue throughout for each cycle

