5.2 Dosage and Administration

Phase 1 Portion

The pamiparib will be taken once on Day 1 of Cycle 1 (morning only), followed by a 1-day treatment-free period (Day 2). Regular daily administration of pamiparib will commence on the morning of Day 3 of Cycle 1, as a 21-day period of repeated drug administration (Days 3 to 23). During subsequent cycles, the patients will take pamiparib BID from Day 1 to Day 21 (with no treatment-free or rest period).

Patients will be required to fast for at least 2 hours before and 1 hour after each administration of pamiparib throughout the study.

Phase 2 Portion

The patients will take pamiparib at 60 mg BID daily from Day 1 of Cycle 1 (with no treatment-free or rest period). Pamiparib capsules will be administered PO BID, once in the morning and once in the evening. The time difference between two consecutive doses will be approximately 12 hours with a window of ± 4 hours. Patients will be instructed to swallow the capsules whole, in rapid succession, with water. Pamiparib can be administered with or without food. However, to reduce gastrointestinal irritation that parmiparib may cause, patients are encouraged to take parmiparib with food.

A dose of pamiparib should be skipped if it is not taken within the upper range of the scheduled time, ie, within 16 hours. An extra dose of pamiparib should not be taken to make up for a missed dose. If vomiting occurs during the course of treatment, no re-dosing of the patient is allowed before the next scheduled dose.

On days with PK assessments, the morning dose of pamiparib should be administered in the clinic in accordance with the schedule for the PK samples.

The toxicity-related treatment delay must be agreed upon by the investigator and the sponsor Medical Monitor.

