# 6.5.2 Extent of Exposure

The number (and percentage) of patients requiring dose reductions, dose interruption, and treatment discontinuation will be summarized. One cycle is defined as 21 days of treatment except for the first cycle in the Phase 1 portion of this study.

The duration of treatment (months) will be summarized with descriptive statistics. It will be calculated as (Date of last non-zero dose – Date of first dose + 1) / 30.4375.

Number of patients with dose reductions and treatment discontinuation and their reasons, as well as number of patients with any dose modification will be summarized by counts and percentages according to study medication data. In addition, frequency of dose reductions and dose interruption will be summarized by categories  $(0, 1, \ge 2)$ .

Average dose intensity per patient (in mg/day) and relative dose intensity (total dose received / total dose planned) per patient will be summarized. Average dose intensity is calculated as the total dose (mg) taken by a patient divided by overall duration of exposure (= Date of last non-zero dose – Date of first dose + 1) for individual patient. Relative dose intensity is calculated as the total dose (mg) taken by a patient divided by the total dose planned for the patient by study design. To note, for the Phase 1 portion of the study, the planned dose for a patient will be a single dose on day 1 at a given dose level, no dose on day 2 and then twice daily for the next 21 days for Cycle 1; and then twice-daily for later treatment cycles. Patients in the Phase 2 portion of the study will always be treated on twice-daily administration at the prescribed dose level.

Patient data listings will be provided for all dosing records.

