#### **ACCUMULATION RATIO**

AUC accumulation ratio is defined as the ratio of AUC at steady state to the AUC for single dose of pamiparib. Accumulation ratio will be normalized for dose level in the following model with repeated measurements for subject i at day j:

$$log(AUC)_{ijk} = \mu + subject_i + dose_j + day_k + dose_i * day_k$$

where the categorical variable, day, distinguishes daily AUC on day 1 (AUCday 1 as single dose) and AUC at steady state (AUCss when dosing day is greater than 1). A subject effect will be included as a random effect. For each dose, the estimate of accumulation ratio will be obtained by applying an exponential function on the difference of least square (LS) means of log(AUCss) and log(AUCday 1). Similarly, a 95% CI for the accumulation ratio will be obtained by applying the exponential function on the 95% CI for the mean of log(AUCss) - log(AUCday 1).

The same analysis will be conducted for  $C_{max}$ .

PK parameters will be analyzed only for Cycle 1. No data beyond Cycle 1 will be included in the analysis. If patient has dose modification (including dose interruption and reduction) from Cycle 1 Day 3 till Cycle 1 Day 10, data on Cycle 1 Day 10 for that patient will not be included in the analysis.

Version 1.1: 02/28/2020 Page 22 of 28

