# DOSE PROPORTIONALITY

Dose proportionality of AUC0-inf, AUClast,ss, Cmax, and Cmax,ss for pamiparib will be assessed using the power model as described below:

$$Log(PK)_i = \alpha + \beta \times log(Dose_i) + \varepsilon_i$$
.

where log(•) is the function of natural logarithm,  $\varepsilon_i$  is a normally distributed random error with mean 0, and PK represents PK parameters AUC, AUClast,ss, Cmax and Cmax,ss. A minimum of 3 values of PK parameters per dose must be available for a given PK parameter. The power model will be estimated by a least square regression method. Point estimates and corresponding 2-sided 95% CIs for the slope parameter and the intercept parameter will be provided.

Dose proportionality will be analyzed only for Cycle 1. No data beyond Cycle 1 will be included in the analysis. If patient has dose modification (including dose interruption and reduction) from Cycle 1 Day 3 till Cycle 1 Day 10, data on Cycle 1 Day 10 for that patient will not be included in the analysis.

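### Protocol 4.1.1 and SAP 6.5.2 disagree on the Phase 1 Day 1 single dose in the 40 and 60 mg cohorts, and the SAP's single-dose PK analyses do not allow for a Day 1 dose that differs from the cohort dose

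*Protocol*

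**What the plan says.** **Day 1 dose.** Protocol 4.1.1 names the levels: "In this study, three dose levels, 20 mg, 40 mg, and 60 mg BID, will be evaluated". It then describes the 23-day first cycle, which "of each dose level will consist of a single administration of pamiparib (20 mg) on the morning of Day 1", followed by a day without drug and 21 days of BID dosing. SAP 6.5.2, defining planned dose for Phase 1 relative dose intensity, has "the planned dose for a patient will be a single dose on day 1 at a given dose level, no dose on day 2". BID dosing starts after that.

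The other protocol descriptions of Day 1 give no separate amount. Footnote 18 of Table 5 reads "A single dose of pamiparib will be administered on the morning of Day 1 of Cycle 1". Section 5.2 says only that the drug is taken once that morning. The synopsis gives single administration as the Day 1 exception to BID dosing, then lists the three levels.

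**Use of the Day 1 profile (SAP 6.6.1).** For accumulation, "AUC accumulation ratio is defined as the ratio of AUC at steady state to the AUC for single dose of pamiparib", with the same analysis for Cmax. The power model for dose proportionality regresses log(PK) on log(Dose) for two single-dose parameters (AUC0-inf, Cmax) and two steady-state ones (AUClast,ss, Cmax,ss).

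**Governing version.** SAP Section 1 refers Phase 1 operation to protocol version 1.1 and the final analysis of both phases to the latest version. SAP Section 8 declares no changes to the planned analysis.

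**The concern.** The Day 1 profile is the denominator of every accumulation ratio and supplies both single-dose proportionality slopes. Both uses need the Day 1 dose to be known, and the ratio needs it to equal the dose behind the steady-state profile. The documents give two different Day 1 doses for the upper cohorts, and neither planned analysis can tell which applied.

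- The accumulation model has one dose factor per cohort, shared by Day 1 and steady state. The SAP says the ratio will be normalised for dose level, but the written model never divides an AUC by the dose given that day.
- The power model does not define Dose as cohort dose or administered dose.
- The exclusion rule covers dose modifications from Day 3 to Day 10 only, so a different Day 1 dose would not trigger it.
- The data check in the power model, "A minimum of 3 values of PK parameters per dose must be available for a given PK parameter", counts values. It does not test whether the dose label is right.

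At stake is the characterisation of PK in Chinese patients, a Phase 1 secondary objective.

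**Working it through.** **Inputs.** Dose levels 20, 40 and 60 mg and a 12-hour interval (Protocol 4.1.1). From Protocol 1.4.1: half-life about 12 h in this study; about 13 h (range 5.4 to 34 h) and about 2-fold accumulation in the first-in-human study; cohort sizes 4, 4 and 7; between-subject variability about 50%.

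**1. Reproduce the stated accumulation.** R = 1/(1 − 2^(−12/t½)).
- t½ = 12 h: R = 1/(1 − 0.5) = 2.00.
- t½ = 13 h: R = 2.12.
- t½ from 5.4 to 34 h: R from 1.27 to 4.61.

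The stated figure of about 2 is reproduced.

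**2. Accumulation ratio under each text.** For each dose the SAP takes exp(LS mean log AUCss − LS mean log AUCday1). Under linear PK, AUCss is proportional to R × cohort dose and AUCday1 to the Day 1 dose. The estimate is therefore R × (cohort dose ÷ Day 1 dose).

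| Cohort | Day 1 at cohort dose | Day 1 at 20 mg |
|---|---|---|
| 20 mg | 2.0 | 2 × 20/20 = 2.0 |
| 40 mg | 2.0 | 2 × 40/20 = 4.0 |
| 60 mg | 2.0 | 2 × 60/20 = 6.0 |

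With R = 2.12, the last column is 2.12, 4.23 and 6.35. The 2-fold and 3-fold inflation applies to Cmax too.

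**3. Single-dose slope under each text.** Least squares of log(PK) on log(Dose), 4/4/7 patients, proportional PK:
- Day 1 at cohort dose: slope 1.00.
- Day 1 at 20 mg, Dose = cohort dose: slope 0.00. In 20,000 simulations at 50% CV, the mean was 0.00 and the SD 0.27, and the 95% CI contained 1 in about 7%.
- Day 1 at 20 mg, Dose = administered dose: log(Dose) does not vary, so the slope is not estimable.

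The steady-state slopes do not use Day 1 and are unchanged.

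**4. Relative dose intensity, Cycle 1, full compliance.** Planned under SAP 6.5.2 is 1 + 42 = 43 administrations at cohort dose.
- 40 mg: planned 43 × 40 = 1720 mg; with 20 mg on Day 1, 20 + 42 × 40 = 1700 mg, or 98.8%.
- 60 mg: planned 43 × 60 = 2580 mg; with 20 mg on Day 1, 20 + 42 × 60 = 2540 mg, or 98.4%.

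**5. Does dose-normalising repair the ratio?** Divide each AUC by the dose given on its day. At 40 mg, 4 × 20/40 = 2. At 60 mg, 6 × 20/60 = 2. Under linear PK it does. Nothing comparable repairs the single-dose slope if every patient had the same Day 1 dose.

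**The case against.** **The current protocol could not have set these patients' first dose.** This stands. Protocol 1.4 reports 15 Phase 1 patients by 25 September 2017, with the Phase 2 dose already confirmed. Version 5.0 is dated 21 September 2018, and Phase 1 ran under version 1.1. A reader might infer from Protocol 4.1.1 that the 40 and 60 mg cohorts received 20 mg on Day 1. The documents do not support that; they do not show what was given. The wording still matters for analysis, because the SAP refers the final analysis of both phases to the latest protocol.

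**The 20 mg may be a carry-over.** It closely follows the sentence on the 20 mg BID starting dose, and no other Day 1 description repeats it. That is plausible, and a reader might conclude that the protocol figure is simply a slip. But the sentence refers to every dose level, and nothing in the documents settles which text is right.

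**Near-proportional exposure is already reported.** Protocol 1.4.1 says AUC rose nearly in proportion to dose, but the Cmax and AUC0-9 figures given by cohort are at steady state. They say nothing about Day 1.

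**The effect is limited.** This also stands. It touches secondary Phase 1 PK summaries only. The Phase 2 response-rate test is not involved, and the dose-intensity shift is under 2 percentage points.

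**Conclusion.** The inconsistency is in the current text, and SAP 6.6.1 cannot absorb it. The consequence is conditional. If Day 1 was 20 mg in all cohorts and PK is linear, the 40 and 60 mg accumulation ratios would be inflated 2-fold and 3-fold (about 4 and 6 instead of about 2). The single-dose slopes would be about 0 on cohort dose, or not estimable on administered dose. If Day 1 was at cohort dose, the planned analyses work as written.

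A reader might go further and call the planned slopes and ratios wrong. The documents do not support that, because the Day 1 dose given is unknown here.

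The sizes rest on linear PK, which the first-in-human summary supports up to 80 mg BID. This study's preliminary steady-state AUC0-9 means are less tidy: 33545/9361 = 3.58 from 20 to 40 mg and 39657/9361 = 4.24 from 20 to 60 mg, in small cohorts that the protocol itself says to read with caution. The exact factors could therefore differ. The point is worth correcting because it is cheap and could make the affected outputs uninterpretable. It does not bear on the trial's primary conclusion.

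**What to change.** 1. Reconcile Protocol 4.1.1 with SAP 6.5.2 without presuming which is right, consulting protocol version 1.1, and check the recorded Day 1 dose of each Phase 1 patient.
2. In SAP 6.6.1, define Dose for single-dose parameters as the recorded Day 1 dose.
3. Before forming the accumulation ratio, divide Day 1 and steady-state AUC and Cmax by the dose given on each day. Use the single administration that starts the profile, not the daily total. State that this assumes linear PK.
4. If the recorded Day 1 dose was the same in all cohorts, drop the single-dose power model as not estimable and report proportionality from steady-state parameters only. Using the recorded dose does not rescue that slope.
5. Keep planned dose in SAP 6.5.2 as the reconciled protocol schedule. Taking it from dosing records would make received equal planned on Day 1 by construction and hide deviations.

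The cost is a clarification of text, a few sentences in the SAP and one derived variable. SAP 6.5.2 already plans listings of all dosing records, so no new data are needed.
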